This study will be a randomized control trial with 2 arms. Patients will be randomized to either the control group (standard fortification) or intervention group (targeted fortification) in a 1:1 allocation ratio. Twins will be considered as one and allocated to the same group. Allocation group will be stratified to four groups according to birth weight: <750g, 751-1000g, 1001-1250g, 1251-1500g. This stratification is based upon our NICU feeding guideline, and will ensure that enrolled infants will receive comparable nutrition progression (e.g. NPO days, days of trophic feeds) throughout the study period. The allocation will be concealed in a sequentially numbered, opaque, sealed envelope, that will be opened after consent is obtained. After randomization, the groups will not be blinded to the investigators or caregivers.

All VLBW infants whose mothers consent to provide breast milk and participate in the study will be included. In the control group, breast milk will be fortified per protocol as listed above and TPN weaned per NICU guideline. The intervention group will receive standard fortification with additional added liquid protein to provide 4 g/kg/day and microlipid to provide 100-130 kcal/kg/day once 100 ml/kg/day of enteral feeds are achieved. Once the infants reach goal enteral feeds of 150ml/kg/day they will continue on the standard or targeted fortification for 4 weeks.

The mothers will provide breast milk when they come to visit their infant in the NICU. They will have access to a pump while visiting in the NICU and lactation consultant will help to arrange for a pump to use at home. They will be provided containers to collect breast milk at home to bring in when they visit their baby in the NICU. Once weekly the mother will collect the previous 24 hours supply of breast milk, which will be homogenized and a sample taken for analysis. The sample will then be analyzed for composition using the Miris human milk analyzer for the carbohydrate, fat, and protein content and caloric density. The remainder of

If this field is not completed your protocol will not be reviewed. Do not enter N/A. Please describe what methods and procedures will be involved in this research.

the milk will be stored as a batch and labelled to feed the infant when he/she is ready.

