Targeted fortification- rare, some babies may have elevated BUN which is routinely monitored in the NICU, or rare, feeding intolerance

Select all that apply.

There is also risk of breach of confidentiality, but this is rare. Data will be stored securely, only key study investigators will have access to data, and it will be deidentified and only the PI will have access to the key.

The probability and magnitude of harm or discomfort anticipated in the

research are no greater than those ordinarily encountered daily during routine care while admitted to NICU.

10.6

Are there defined stopping rules? Yes No

Describe in enough detail for the IRB to assess safety.

What are the stopping rules for the study? What are the conditions under which a subject will be withdrawn from the study for safety reasons, i.e. disease progression?

Intolerance to fortification, excessive emesis or recurrent, otherwise unexplained, abdominal distention.

What findings, events, or conditions would require a research subject to be removed from the study? (i.e. disease progression)

Clinical worsening, acute decompensation of infant precluding them from receiving enteral feeds.

If a patient become acutely ill and significantly decompensates they may be removed from the study. Ex: sepsis, abdominal distention, blood in the stool, respiratory failure with increasing need for respiratory support. If a patient becomes comfort-care only and no longer receiving enteral feeds they may also be removed from the study.

10.7

What Category of risk will study participants be exposed too?

Name

[Privacy](#)

[Other](#)

Should be consistent with risks listed in the Consent Form.

10.8

If Other listed above please specify:

Infants will need to leave the NICU for PEAPOD body composition measurement. This will be done once they are determined to be medically stable and ready for discharge.

A text box is provided for further explanation.

A text box is provided for further explanation.

10.9

Describe the availability of medical or psychological services that participants might require as a consequence of participation in this the research:

The participants will have medical services available in the NICU at their disposal during the entirety of involvement in the study. Every effort will be made to obtain resources to support mother's pumping activities and providing of breast milk- pumping room with breast pumps and supplies, lactation services, nutrition services.

10.10

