*** Note More Frequent monitoring intervals may be needed for vulnerable populations.**

4.A. Plan for Adverse Event Reporting:

All Reportable Events (Anticipated and Unanticipated events) from this protocol must be submitted using the MHA eIRB Reportable event form in a timely maner consistent with MHS IRB SOPs.

In addition to the MHS IRB adverse events and Uanticipated problems will be reported to:

Reporting Institutions (check all that apply):

Name

There are no items to display

If other has been selected above please specify:

4.B Stopping Rules or Conditions under which Subjects can be removed from the Study [this information is from Section 10.01 of the Protocol Risks/Benefits Questions

Are there defined Stopping Rules? Yes

What are the stopping rules for the study? Intolerance to fortification, excessive emesis or recurrent, otherwise unexplained, abdominal distention.

What findings, events, or conditions would require a research subject to be removed from the study? (i.e. disease progression)

Clinical worsening, acute decompensation of infant precluding them from receiving enteral feeds.

If a patient become acutely ill and significantly decompensates they may be removed from the study. Ex: sepsis, abdominal distention, blood in the stool, respiratory failure with increasing need for respiratory support. If a patient becomes comfort-care only and no longer receiving enteral feeds they may also be removed from the study.

4.D. Additional Information (if Applicable):

Provide any other information relevant to the data and safety monitoring plan that was not already incorporated into this form.

Attach A copy of your Data Safety Monitoring Plan or other relevant information related to this form:

Name

Version

There are no items to display

View: 19-00 Use of Human Biological Materials In Research I

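### Section 10.6 takes infants out of the study, not only off fortification, for intolerance or acute illness, and nothing supplied keeps their outcomes in follow-up or in an as-randomised analysis

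*Combined protocol and SAP*

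**What the plan says.** Section 10.6 has two form questions and the investigators' answers.

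- The first question asks: "What are the conditions under which a subject will be withdrawn from the study for safety reasons". The answer is: "Intolerance to fortification, excessive emesis or recurrent, otherwise unexplained, abdominal distention".
- The second asks: "What findings, events, or conditions would require a research subject to be removed from the study". The answer begins: "Clinical worsening, acute decompensation of infant precluding them from receiving enteral feeds". It goes on: "If a patient become acutely ill and significantly decompensates they may be removed from the study", with sepsis, distention, blood in the stool and respiratory failure as examples. It ends: "If a patient becomes comfort-care only and no longer receiving enteral feeds they may also be removed from the study".

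Item 4.B of the data safety monitoring plan repeats these answers. It is filled from the same place ("this information is from Section 10.01 of the Protocol Risks/Benefits Questions"), so it is not independent support, and it adds nothing on follow-up.

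On protection against bias, section 8.4 says: "The allocation will be concealed in a sequentially numbered, opaque, sealed envelope, that will be opened after consent is obtained". After randomisation, investigators and caregivers know the arm. The CRU staff who run the PEAPOD are blinded.

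The primary outcome (section 7.2) is one body composition measurement, taken 4 weeks after full feeds or at NICU discharge, whichever is earlier. Sections 8.4 and 10.1 describe the pre-discharge PEAPOD and the weekly anthropometry as standard care. Section 10.3 lists the outcomes and a sample-size statement. It names no analysis set, no test and no rule for missing data.

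**The concern.** Both questions in section 10.6 concern leaving the study. The plan does not separate that from stopping the added protein and lipid. An infant removed before the late PEAPOD has no stated route to contribute the primary outcome, and no analysis set says whether that infant counts.

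The grounds for removal arise after randomisation and are likely to be related to growth. Some may also be related to arm. Section 10.5 lists feeding intolerance as a risk of targeted fortification, and only that arm receives added liquid protein and microlipid, so a link is plausible for intolerance, distention and blood in the stool. A link is also possible through discretion, because the wording for acutely ill infants is permissive and those around the infant know the arm. No mechanism by arm is evident for sepsis or respiratory failure.

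If the targeted arm loses more poorly growing infants, the comparison tilts towards targeted fortification. If the control arm does, it tilts the other way. Concealed envelopes and a blinded PEAPOD operator do not protect against loss after randomisation.

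**Working it through.** The textual part needs no arithmetic: sections 7.2, 8.4, 10.1, 10.3, 10.6 and 4.B contain no sentence on collecting outcomes after removal and none on analysis as randomised.

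The size has to be illustrated, because the documents give no removal rate by arm.

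**Inputs from the plan.** Target difference 0.5 in fat-free mass z-score, alpha 0.05, 80% power, 25 per group (section 10.3); 60 enrolled at 1:1, taken here as 30 infants per arm (sections 11.2 and 8.4); 'rare' defined as 1% or less and applied to feeding intolerance (section 10.5).

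**Inputs assumed.** The removal rates; a correlation ρ of 0.3 to 0.5 between removal and fat-free mass; a two-sided t-test.

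**The plan's own figure.** The 25 per group cannot be reproduced, because no SD is given. Solving backwards, a two-sided t-test with 25 per group and 80% power needs d = 0.809, so SD = 0.5 / 0.809 = 0.618. One-sided, the implied SD is about 0.70. An SD of 1 is not used, since 25 per group would then have about 41% power.

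**Shift in one arm's mean.** If a fraction f is removed according to a score correlated ρ with the outcome, the mean of those left moves by ρ·φ(z_f)/(1 − f) SD. At ρ = 1 this is 0.0269 for f = 0.01, 0.1086 for f = 0.05 and 0.1950 for f = 0.10. The bias is the difference between arms, multiplied by ρ and then by 0.618 to give z-score units. For 10% v 0%: 0.3 × 0.1950 = 0.0585 SD and 0.5 × 0.1950 = 0.0975 SD.

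| Removed, one arm v other | Shift (SD) | Shift (z-score) | Share of 0.5 | Type I error |
|---|---|---|---|---|
| 1% v 0% | 0.0081-0.0135 | 0.0050-0.0083 | 1.0-1.7% | 5.0% |
| 10% v 5% | 0.0259-0.0432 | 0.0160-0.0267 | 3.2-5.3% | 5.1-5.3% |
| 10% v 0% | 0.0585-0.0975 | 0.0362-0.0603 | 7.2-12.1% | 5.5-6.5% |
| Equal and equally outcome-related | 0 | 0 | 0% | nominal |

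Type I error is from the noncentral t, with 30 v 30, 27 v 28.5 and 27 v 30 analysed in the first three rows. Simulation of the 10% v 0% case gave shifts of 0.060 and 0.099 SD and rejection rates of 5.4% and 6.7%.

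**Sensitivity to the SD.** At the one-sided SD of 0.70, the 10% v 0% shift is 0.0585 × 0.70 = 0.041 to 0.0975 × 0.70 = 0.068, or about 8-14% of the target.

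**The case against.** The strongest reply is that no data loss is stated. The PEAPOD and anthropometry are routine for these infants, and section 14.3 draws data from the medical record, so outcomes would normally exist for infants who recover. That stands, and it is why the fix is cheap. But routine measurement is not a commitment to collect or analyse after removal.

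A reader might infer that the plan excludes removed infants from analysis. The documents do not say so; they leave it open. The consent and HIPAA form attached at section 17.15 was not available and may cover data use after withdrawal.

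A reader might also infer a plain contradiction between required and optional removal. The words on requirement belong to the form's pre-printed question; the investigators wrote only the answer. It can be read as two tiers, with some overlap for infants no longer on enteral feeds. That calls for clarification and is not the main point.

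The documents do not say who decides removal. Section 18.01 names a person under the item on a medical monitor or independent safety officer, without saying that this person is blinded or decides removals. Unblinded discretion is therefore possible, not established.

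Controls also receive fortifier and can be intolerant of it, so 10% v 0% is a severe case. At the documents' own ceiling for feeding intolerance, 1%, the bias is negligible. That ceiling does not cover sepsis, respiratory failure or discretionary removal. The 10 places above the required 50 are not described as a dropout allowance, and spare numbers would not correct selective loss.

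**Conclusion.** The concern holds as a gap between removal and follow-up. The plan takes infants out of the study for events after randomisation, with investigators and caregivers unblinded, and says neither that their outcomes are still collected nor that they are analysed as assigned. This can lose the single late primary measurement selectively.

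The likely effect is small, and it rests on assumed removal rates, an assumed correlation of 0.3 to 0.5 and an SD back-solved from the sample size. The documents do not support a claim that the result will be biased towards targeted fortification: the direction depends on which arm loses more poorly growing infants, and equal, equally outcome-related removal gives no bias. This is a cheap improvement, held with medium confidence.

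**What to change.** Leave every clinical criterion and every decision about fortification as it is.

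- **Section 10.6 (4.B follows from it).** Separate stopping study fortification from leaving the study. State that infants who stop stay in follow-up unless the parent withdraws permission. Collect routine anthropometry, and the standard-of-care PEAPOD at the section 7.2 time point where the infant is stable enough, otherwise before discharge with the timing recorded. The investigators should clarify which removals are mandatory and which are discretionary.
- **Section 10.3.** State that all randomised infants with a PEAPOD are analysed in their assigned arm, and that removals, deaths and missing PEAPODs are reported by arm with reasons.
- **Consent form.** Check that it agrees.

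The cost is a few sentences and no new procedure. The downside is dilution. If 10% of the targeted arm stop and gain nothing, a true 0.5 becomes 0.9 × 0.5 = 0.45, and power with 30 per arm at SD 0.618 falls from 86.9% to 79.2%. Dropping those infants instead (27 v 30) would give 85.0% at a difference of 0.5, but would carry the selection risk. The dilution of 0.05 is similar in size to the 0.036-0.060 bias in the 10% v 0% case, so the gain is a comparison that keeps the randomised groups, not extra power. The sickest infants will still lack a PEAPOD, because section 10.8 requires a medically stable infant.

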12.0 Study Participant Information II:**12.1 Select age range of study participants:**

Subject Age Range

0 - 6

12 - 17

18 - 64

Check all that apply.

12.2

* Will the study enroll vulnerable subject groups?

Yes

* Will you be enrolling Children?

Yes No

* Will you be enrolling Pregnant Women and/or Fetuses?

Yes **No**

* Will you be enrolling decisionally impaired subjects?

Yes **No**

* Will you be enrolling Prisoners? Yes **No**

Check yes or no.

12.3 Please identify any vulnerable populations participating in the study:

Vulnerable Populations

Poor / Uninsured

Minors - Children under 18

Employees

Students

Minorities

Check all that apply.

12.4 If you selected "other" above please describe:

Please describe other.

If you are going to enroll any vulnerable populations please describe the safeguards you will put in place to protect these vulnerable Populations.

Please enter a detailed plan.

12.5

Informed consent will be obtained from the mother prior to enrollment of the premature infant. They will be informed that participation in the study is optional and their decision will not impact the medical care that the infant receives.

View: Supplemental Review Form for Research with Children I

Supplemental Review Form for Research with Children I:

Federal regulations require the IRB to provide additional protections for children involved as subjects in research. There are four categories of permissible research that involve children [45 CFR 46.404, 46.405, 46.406, or 46.407]. **Please complete each section as it applies to your research. Each question must be fully answered, or your study will be returned and IRB review will be delayed.**

ASSESSING RISKS AND BENEFITS

When assessing risks and benefits, consider the variability in health status of the subjects to be enrolled, their medical experiences, and the extent to which the research procedures will be a burden to the subjects in the context of their daily lives and/or routine medical care. Be sensitive to how a procedure that generally entails little to no physical or psychosocial risks may affect someone with limited (or no) understanding of the situation. Procedures that usually present no more than minimal risk to a healthy child include: physical exam, ultrasound, urinalysis, obtaining a small amount of blood, EEGs, allergy scratch

tests, minor changes in diet or daily routine, and/or the use of standard psychological or educational tests. The assessment of the probability and magnitude of the risk, however, may be different in sick children and may vary depending on the diseases or conditions the subjects may have.

Minimal Risk: As defined in the regulations 45 CFR 46.102(i), "minimal risk" means the probability and magnitude of harm or discomfort anticipated in the research are not greater in and of themselves than those ordinarily encountered in daily life or during the performance of routine physical or psychological examinations or tests."

Answer 1, 2, 3, or 4 below if applicable:

1. Is this Pediatric Research not involving greater than minimal risk (see definition above) [45 CFR 46.404]:

Yes No

Explain Why you think this study is not greater than minimal risk:

We will be fortifying breast milk with protein and fat to provide individualized nutrition based on human milk analysis to meet nutritional goals and optimize premature infants growth. We will be using liquid protein and microlipids which are approved for neonatal use. Optimizing nutrition will potentially have a beneficial effect on growth, medical, and developmental outcomes.

No medications or other potential harmful substances are given. The probability and magnitude of harm or discomfort anticipated in the research are not greater than those ordinarily encountered in daily life or during routine care in the NICU.

2. Is this Pediatric Research involving greater than minimal risk but presenting the prospect of direct benefit to individual subjects [45 CFR 46.405]. Answer all questions below. Yes No

Explain why you think the procedures or interventions are of greater than minimal risk:

Describe the anticipated or possible health benefits, and explain why you think the study interventions or procedures hold out the prospect of direct benefit to each individual subject:

Explain why you think the risk to subjects is justified by the anticipated benefit:

Explain why you think the risk/benefit ratio is at least as favorable to the subjects as that presented by available alternative approaches:

3. Research involving greater than minimal risk and no prospect of direct benefit to individual subjects, but likely to yield generalizable knowledge about the subject's disorder or condition. [45 CFR 46.406]. Answer all questions below:

Yes No

Explain why you think the interventions or procedures represent no more than a minor increase over minimal risk:

Explain why you think the interventions or procedures present experiences to subjects that are reasonably commensurate with those inherent in their actual or expected medical, dental, psychological, social, or educational situations:

Explain why you think the interventions or procedures are likely to yield generalizable knowledge about the subjects' disorder or condition that is of vital importance for the understanding or amelioration of the subjects' disorder or condition:

4. **Is this Pediatric research that is, not otherwise approvable that presents an opportunity to understand, prevent, or alleviate a serious problem affecting the health or welfare of children [45 CFR 46.407]. This category includes research that does not meet the criteria for any of the above three risk/benefit categories. Research in this category represents more than a minor increase over minimal risk and no prospect of direct benefit to subjects.**

Yes **No**

Explain why you think the research presents a reasonable opportunity to further the understanding, prevention, or alleviation of a serious problem affecting the health or welfare of children:

NOTE: This kind of research requires review by the Secretary of DHHS, after consultation with a panel of experts in pertinent disciplines, and public review and comment. Contact the Manager and Chair of the MHS IRB at [contact], if you believe your research falls into this category.

View: Supplemental Review Form for Research with Children II

Supplemental Review Form for Research with Children II:

SECTION 2: PERMISSION OF PARENTS/GUARDIANS AND ASSENT OF CHILDREN

5. **Permission of Parents or Guardian (check one below)**

The permission of both parents or a guardian(s) will be sought unless one parent is deceased, unknown, incompetent, or not reasonably available, or when only one parent has legal responsibility for the care and custody of the child (required for categories 45CFR.406 & 407 see questions [3] and [4]).

or

The permission of only one parent will be sought (acceptable for categories 45CFR46.404 & 405 see questions [1] and [2]).

INSTRUCTIONS: Check all that apply and answer the related questions.

6. **Assent of Children (check one below)**

The assent of each child who is capable of providing assent based on age, maturity, and psychological state will be sought.

or

The assent of each child will not be sought because the capability of all of the children in this study population is so limited that they cannot reasonably be consulted.

Explain why the capacity is so limited, e.g., age, maturity and/or psychological state:
Age- premature infants, from birth until hospital discharge approximately 3-4months old

or

The assent of each child will not be sought because the intervention or procedure involved in the research holds out a prospect of direct benefit that is important to the health or well-being of the children and is available only in the context of the research.

Explain what the direct benefit may be and why it is only available in the context of the research:

NOTE: Ohio law generally permits individuals to consent for their own medical care at age 18, but limited exceptions permit individuals to consent at an earlier age to certain treatments. Consult the MHS Policy I-34 on the MIV.

View: 13-00 Recruitment I

13.0 Recruitment I:

All external advertisements (for radio, print media or TV) must be approved by MHS Communications Department prior to submission to the IRB so the IRB can see the final advertisement or script. All Advertisements on the MIV or On Hold messaging must be approved by the IRB before they are placed. You may not advertise a study which is not approved by the IRB. Please note that all studies which have a contract which an external sponsor must have that contract signed before any advertising can be done.

13.1

Recruitment Methods/Sources:

Check all that apply.

Name _____

None

13.2 If "Other" checked in 13.1 please explain:

Please explain what other means.

13.3 Describe in detail all recruitment strategies for each subject group (as listed in Section 11.0) selected for this research:

Please describe recruitment strategies in detail.

Recruitment is from all deliveries at MHMC with birth weight less than 1500 grams. The NICU admission log will be consulted. Mothers of infants fulfilling the inclusion criteria will be approached and informed consent will be obtained for enrollment into the study. Mothers will be approached while in labor and delivery once they are stable or when they visit the infant in the NICU and able to comprehend the informed consent process.

13.4 What measures will be taken during the recruitment process to safeguard against the potential coercion or appearance of coercion of human subjects, particularly vulnerable subject groups?

Please give an explanation of safeguards to be used.

Mothers will be given ample time to read and review the informed consent and discuss with close family and friends. They will also be told that participation in the study is not required and it will not impact their care.

13.5 Incentives to Subjects: Will subjects receive any incentives (payments, free service, gifts, etc.) for participation in the research?

This information must mirror the consent form language.

No

13.6 If yes, please describe these incentives and how they will be disbursed:

Note: payment or compensation to subjects for participation is not to be considered a potential benefit.

Describe incentives, if they are to be pro-rated based on visits completed please give that information. This information must mirror consent form language.

13.7 Please attach copies of all recruitment/advertising materials and verbal scripts:

Attach copies of all recruitment and advertising materials.

Name

Version

There are no items to display

View: 13-01 Recruitment II

13.1 Recruitment II:

13.8 Expense to Subjects: Will subjects incur any expenses as a result of participation in the study or will they be billed for any study-related procedures?

Check yes or no, make sure this information is in the consent.

No

13.9 If yes, please describe the expenses or charges that subjects will be assessed:

Please provide information regarding expenses to subjects and add information to consent.

13.10 Compensation For Injury: If applicable, will funding be available to compensate subjects for injuries sustained as a result of participation in

Check yes or no, make sure this information is in the consent.

this research?

No

13.11 Who will cover the costs related to any injuries sustained due to participation in the study?

Please describe in detail. Examples subjects or their insurance company, study sponsor.

View: 14-00 Data Collection

14.0 Data Collection:

14.1

A. What type of data will you be collecting as part of this research?

Existing data must be in place or on the shelf prior to the submission of the research protocol to the IRB.

Will you collect existing data?

Prospective data is collected in real time.

or

Will you collect prospective data?

Yes No

or

Will you collect both existing and prospective data? Yes No

Definitions: Data are considered to be existing data only if they were in place or "on the shelf" prior to the submission of the research protocol to the IRB. Data are considered prospective if they are created and collected as part of the research i.e. from surveys, questionnaires.

Tell the IRB why you are collecting this data i.e. to verify inclusion criteria.

B. Why are you collecting this data?

What will be the purpose of collecting and/or reviewing the data (new data or existing data).

After intervention of targeted fortification vs standard fortification anthropometric measurements and body composition will be measured. Daily weight; weekly length, head circumference, skinfold thickness or mid upper arm circumference; and PEAPOD body composition prior to discharge. These will be measured to evaluate growth parameters of infants receiving individualized targeted fortification to meet nutritional goals vs standard fortification.

14.2

If you are collecting existing data:

Specify the types of existing data you will use in this study.

Specify the type(s) of existing data sources you will use (medical records, school records, publicly available records, existing database). If you are collecting data from an existing database and that database contains PHI, you must provide the IRB Approval letter (attach to Section 27.00 Additional Documents).

We will use medical records for mother and baby to obtain demographics.

Time frame i.e. last 10 years or from 1990-2000.

What is the timeframe of the existing data you wish to review? (i.e. 2000-2006)

Any time before study enrollment.

14.3

If you are collecting prospective data:

Where or how will the data be obtained? (i.e. surveys, questionnaires, psychological tests)

Where will data be obtained? i.e. survey.

NICU admission log and electronic medical records. Milk samples will be analyzed in the lab at MHMC using the Miris human milk analyzer. PEAPOD body composition measurements will be done at the CRU.

14.4

How will the data you collect be identified?

Types of Data Identification:

Name

Deidentified/Confidential- Data will be linked to subject(s) via a code or indirect identifier (i.e. study IDs or numbers)

*Please select how your subject data will be identified.***14.5 Will the information collected from these records be linked to any research subjects by identifiers? (i.e. name, MRN#, DOB)** Yes No*Will your data be linked to subjects?**Please answer questions about the security of the data in section 15.00***14.6 If subject data will be deidentified using a code will there be a link or a key? Please describe. Who will have the key and where will the key be kept?**

Each patient in the database will be assigned a sequential subject number. Medical record number will be in the key only, not in the database. The key will be kept in REDCap and the deidentified data will be kept on a secure MHS network drive. Only the PI and coinvestigator will have access to the key.

Explain how Data will be linked.

Under the HIPAA Regulations, deidentified key codes must be stored separately from data & must not be kept on paper, but electronically. The MetroHealth Research Informatics Support should be contacted at [contact] for assistance. They will assist personnel in developing a key in MetroHealth REDcap database. They can also assist with training & development for your study. REDcap is a free database provided in part by the Case CTSA.

14.7 Data Collection Form(s):

Name

data sheet HMA revised.xlsx | History

Version

0.01

Add data collection forms and CRFs.

View: 15-00 Data Security I

15.0 Data Security I:**It is imperative that the IRB is proactive and consistent in protecting all research data containing Protected Health Information (PHI).****15.1 * Are the records for this study (some or all) electronic?** Yes No

What is Protected Health Information? The Privacy Rule protects certain information that covered entities use and disclose. This information is called protected health information (PHI), which is generally individually identifiable health information that is transmitted by, or maintained in, electronic media or any other form or medium. This information must relate to 1) the past, present, or future physical or mental health, or condition of an individual; 2) provision of health care to an individual; or 3) payment for the provision of health care to an individual. If the information identifies or provides a reasonable basis to believe it can be used to identify an individual, it is considered individually identifiable health information.

The following questions must be answered when submitting a new protocol.**15.2 * Are you collecting PHI?** Yes No**15.3 Is any PHI going to be stored as paper files?** Yes No**15.4 Is any PHI going to be stored in an electronic file format? (i.e. access, excel)** Yes No**15.5 Is your data being stored on a laptop computer?** Yes No**15.6 Will you be using RedCap to store your data?** Yes No**Which RedCap Database will you be using?**

Name

Name

MetroHealth

15.7 Are you planning to store your data using a portable storage device?(i.e. jump drive, external hard drive, cd) Yes No

**Per current MetroHealth Policy PHI may not be stored on portable electronic devices.*

15.8 Are there any circumstances under which you would want to remove data from MHS? (i.e. take data home to work on it) Give details below. Please note identified data can't be removed from MHS unless there is permission granted in the HIPAA Authorization. If you are unsure about what is identified data please consult the IRB staff. If you feel you will need access to your data when you are off campus you should ask the MHS IT Department located in Rammelkamp room R 134 about VPN access.

Yes No

If you answered yes to question 15.8, please explain?

15.9 Where will the records pertaining to this research be stored? (give the actual physical location of the paper records i.e building name and room number); and/or the secure network drive where the data is being stored.

Records will be stored electronically on the shared secure network drive of the MetroHealth network.

REDCap(Research ElectronicData Capture) is a secure, web application designed to support data capture for research studies, providing user-friendly web-based case report forms, real-time data entry validation (e.g. for data types and range checks), audit trails and a de-identified data export mechanism to common statistical packages (SPSS, SAS, Stata, R/S-Plus). The system was developed by a multi-institutional consortium which includes The MetroHealth Medical Center and was initiated at Vanderbilt University. The database is hosted at the MetroHealth Datacenter. The system is protected behind a login and The MetroHealth Firewall. There is an audit trail tracking all logins and activities in the database. Data collection is customized for each study or clinical trial based on a study-specific data dictionary defined by the research team with guidance from the REDCap administrator.

State the exact physical location of paper files and the network drive for electronic files.

15.10

How will these records be secured (we are referring to both paper records and electronic records)? Examples for electronic records (i.e. secure drive, password protected documents, encrypted jump drive). Examples for paper records, must be double locked (i.e. locked office and locked file cabinet or a locked file box inside a locked cabinet).

Records will be stored electronically on the shared secure network drive of the MetroHealth network, which will require a password to retrieve which only the study team will have access to. Only the study team will have access to REDcap, which will require a password to access.

i.e. locked cabinet, locked room.

